7.7.2.5 Sensitivity Analysis

For the primary endpoint, the subsequent sensitivity analysis will consist of all studies that meet the eligibility criteria described above without regard to sample size or completeness of data ([Table 3](#)). This yields 9 clinical trials for K monotherapy totaling 604 subjects and 9 clinical trials for Kd totaling 1,213 subjects.

Table 3. Clinical Trials for Sensitivity Data Analysis

K27 (559 subjects)	K56 (45 subjects)	Kd27 (586 subjects)	Kd56 (627 subjects)
20140122 (7 subjects)	20130402 (2 subjects)	20140355 (235 subjects)	20160275 (153 subjects)
20140120 (8 subjects)	20130401 (19 subjects)	20140242 (123 subjects)	20130398 (463 subjects)
20140119 (78 subjects)	20130393 (24 subjects)	20140122 (3 subjects)	20130393 (8 subjects)
20140118 (200 subjects)		20140120 (20 subjects)	20130401 (3 subjects)
20130396 (157 subjects)		2011-002 (205 subjects)	
20130401 (4 subjects)			
2011-002 (105 subjects)			

7.7.2.5.1 Subgroup Analysis

Exploratory subgroup analyses may be performed based on the following subgroups determined by the covariates (clinical parameters), if applicable, as per [List 1](#). If there is an insufficient number of subjects in a particular subgroup, defined as less than 10% of subjects in that particular carfilzomib dosing regimen, relevant subgroups may be combined.

7.7.3 Analysis of Safety Endpoint(s)/Outcome(s)

Please refer to [Section 7.7.2.4](#) for the description of the efficacy and safety analyses. The Medical Dictionary for Regulatory Activities (MedDRA) version 23.0 or later will be used to code all events.

7.8 Quality Control

Biostatistical programmers will write and execute the analytics. A programmer will be assigned to quality control and verify the results from the analyses.

7.9 Limitations of the Research Methods

7.9.1.1 Confounding

All the clinical parameters specified in List 1 are considered to be potential important confounding variables, given the potential association with both the specific K dosing regimens and efficacy and/or safety outcomes. In the analyses of comparison between

the dosing regimens, the propensity score matching method will adjust for the covariates by balancing out their distributions between the dosing regimens.

7.9.2 Analysis Limitations

This is a post-hoc pooled analysis to evaluate the benefit-risk profile of the clinical parameters that are associated with efficacy and safety outcomes for each K dosing regimen (K27, Kd27, K56, Kd56) which may inform the choice of carfilzomib dose. To balance the clinical parameters between non-randomized dosing regimens, and thereby reduce bias due to patient selection given that subjects might differ systematically between dosing regimens, the well-established propensity score matching method will be used ([Brookhart et al, 2006](#); [D'Agostino, 1998](#)). While there are inherent limitations to the propensity score matching method, including the loss of patients who cannot be matched 1:1 and inability to create a balance for unobserved covariates, there are no superior alternative methods to adjust for differences in populations among the various clinical trials to enhance the robustness of the results. Therefore, at this time, this method is considered the most appropriate method to compare the clinical outcomes overall and in subsequent subgroups.

In response to the anticipated variations in the sample sizes and data variables collected for these 13 clinical trials, and to avoid the introduction of extra-variation to the pooled data, there will be a primary analysis and a subsequent sensitivity analysis, as previously described in [Section 7.7.2](#).

Another limitation is the small sample size of the pooled data for K56. The small sample size prevents robust comparison of K27 vs K56, which is needed to summarize potential clinical parameters that could impact the choice between these two regimens.

Supplementation of K56 data from real-world clinical databases would introduce significant volumes of missing data, which would compromise the integrity of the post-hoc analysis. To probe further and better understand carfilzomib monotherapy, which may be a plausible option for subjects with heavily pre-treated myeloma, an exploratory analysis will be performed to compare the efficacy and safety outcomes for K27 dosing regimen without versus with dexamethasone (K27 versus Kd27).

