5.1 Diseases and Therapeutic Area

Multiple myeloma is the second most common hematological malignancy with more than 150,000 new diagnoses per year globally ([Bray et al, 2018](#)). Certain populations are at higher risk of developing MM, namely the elderly with the peak number of new diagnoses in individuals aged 65 to 74 years. African Americans are twice as likely to develop MM than Caucasian-Americans. Men are slightly more likely to develop MM compared to women ([Ailawadhi et al, 2019](#)). As the most common malignant plasma cell disorder, MM is characterized by neoplastic proliferation of a predominant clone of plasma cells that produce a monoclonal immunoglobulin protein. Each person with MM

tends to harbor subclones of plasma cells, which can evolve and mutate. This genetic heterogeneity of abnormal plasma cells is hypothesized to drive disease progression and treatment resistance. As a result, MM is characterized by periods of remission and relapse, but remains ultimately fatal ([Durie, 2018](#)).

The introduction of novel treatment agents has revolutionized the treatment landscape such that the median survival now extends to approximately 5 years ([SEER Database 2010-2016](#)). One of the novel treatment agents is K, a second-generation proteasome inhibitor (PI) that the FDA granted accelerated approval in 2012 for use in individuals with RRMM. Phase 1 studies with K noted better tolerance when administered 2 consecutive days at the start of each week for three weeks of each four-week cycle compared to 5 consecutive days at the start of each two-week cycle. As monotherapy, K at a dose of 27mg/m² demonstrated efficacy. The absence of a maximally tolerated dose led to subsequent escalation studies, which suggested improved efficacy without significant additional toxicity at a dose of 56mg/m² when infused over a duration of 30 minutes instead of 10 minutes, a regimen which was also approved by the FDA. When combined with the therapeutic dose for dexamethasone, Kd demonstrated improved efficacy with a comparable safety profile to previous phase 1 and 2 trials. It was the pivotal phase 3 ENDEAVOR clinical trial that established K 20/56 with dexamethasone (Kd 20/56) as a cornerstone for treatment in RRMM ([O'Connor et al, 2009](#); [Packet insert for Kyprolis, 2019](#); [Goren et al, 2019](#)).

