6.2 Secondary

Compare efficacy and safety outcomes for K dosing regimens with dexamethasone (Kd27 versus Kd56)

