7.3.4 Rationale of Variable Pertaining to Treatment Patterns: Year of treatment initiation

It is recognized that the implementation of these Amgen acquired or sponsored clinical trials spanned nearly a decade, whereby the understanding of the myeloma disease greatly has improved and the clinical development of K proceeded from preclinical to robust clinical studies. As the RRMM treatment combinations and patterns are dynamic, an additional clinical parameter to consider is the year of treatment initiation.

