7.7.1.1 Primary Analysis

In response to the anticipated variations in the sample sizes and data variables collected for these 13 clinical trials, there will be a primary analysis and a subsequent sensitivity analysis to avoid the introduction of extra-variation to the pooled data. The primary analysis will consist of all studies that meet the eligibility criteria with an adequate sample size of at least 20 subjects and at least 80% completeness of data for each variable in [List 1](#) (Table 2). This yields 5 clinical trials for K monotherapy totaling 564 subjects and 6 clinical trials for Kd totaling 1,199 subjects.

Table 2. Clinical Trials for Primary Data Analysis

K27 (540 subjects)	K56 (24 subjects)	Kd27 (583 subjects)	Kd56 (616 subjects)
20140119 (78 subjects)	20130393 (24 subjects)	20140355 (235 subjects)	20160275 (153 subjects)
20140118 (200 subjects)		20140242 (123 subjects)	20130398 (463 subjects)
20130396 (157 subjects)		20140120 (20 subjects)	
2011-002 (105 subjects)		2011-002 (205 subjects)	

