7.7.2.4 Analysis of the Primary, Secondary, and Exploratory Endpoint(s)

For the primary endpoint, the analyses will describe the distribution of each clinical parameter and the distribution of each efficacy/safety outcome by each dosing regimen (K27, Kd27, K56, and Kd56) to yield a summary of the favorable versus unfavorable effects for each dosing regimen.

For the secondary and exploratory endpoints, the outcomes for efficacy will use the well-established endpoints of PFS, an approved surrogate marker of overall survival, and ORR, one of the most commonly used endpoints in myeloma clinical trials. Each individual trial will follow its own definition of PFS and ORR, which was specified in its respective SAP, to derive these pooled data. For analyses of PFS, Kaplan-Meier estimates will be used to estimate the median and other quartiles along with corresponding two-sided 95% confidence intervals. For analyses of ORR, the associated 95% exact binomial confidence interval (Clopper-Pearson method) will be

reported for Kd56 versus Kd27 and Kd27 versus K27. Risk ratio (RR) with the corresponding 95% CIs for Kd56 versus Kd27 and Kd27 versus K27 will be estimated using Cochran-Mantel-Haenszel (CMH) method. To account for potential differences in drug exposure duration, exposure-adjusted incidence rate with the corresponding 95% CI will also be calculated.

Also, for the secondary and exploratory endpoints, outcomes for safety will use endpoints of all fatal events as well as grade 3 or higher and serious adverse events (AEs) of special interest (List 2). Classification of the severity of AEs from each trial will be in accordance with the NCI-CTCAE criteria used during that individual clinical trial, which was also specified in its respective SAP. The number and percentage of subjects experiencing the treatment-emergent adverse event (TEAE) by system organ class/preferred term (SOC/PT) will be summarized for the specified safety outcomes and presented side-by-side for the 4 dosing regimens (K27, K56, Kd27, Kd56) overall for both the primary and sensitivity analyses.

List 2. Adverse Events of Special Interest (in alphabetical order)

- Acute renal failure (SMQN)
- Cardiac events (Sum of events for cardiac failure [SMQN] + ischemic heart disease [SMQN] + torsades des points including QT prolongation [SMQB])
- Cardiac failure (SMQN)
- Hypertension (SMQN)

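### No trial supplies both Kd27 and Kd56, so the secondary comparison is a between-trial contrast that matching on List 1 cannot turn into a dose effect, and Section 7.9.2 does not say so

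*Protocol*

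**What the plan says.** Protocol Section 6.2 sets the Kd27 versus Kd56 comparison of efficacy and safety as the secondary objective. Section 7.2.2 builds the propensity score from the List 1 covariates and matches 1:1 within a caliper of 0.1 standard deviations of the logit. List 1 has no trial identifier. The nearest thing to one is calendar time, for which Section 7.3.4 says "an additional clinical parameter to consider is the year of treatment initiation".

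Section 7.7.2.4 lets each trial keep its own PFS and ORR definitions and its own CTCAE criteria. It names Kaplan-Meier intervals for PFS and Clopper-Pearson intervals for ORR. Risk ratios "will be estimated using Cochran-Mantel-Haenszel (CMH) method", with no strata given. The matched comparisons are to report a hazard ratio, odds ratio and risk ratio with confidence intervals, overall and in List 1 subgroups. Details are left to SAP Sections 9.5 and 9.6.

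Section 7.7.2.5 describes one sensitivity analysis, introduced for the primary endpoint, that drops the sample-size and completeness criteria: "This yields 9 clinical trials for K monotherapy totaling 604 subjects and 9 clinical trials for Kd totaling 1,213 subjects".

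Section 7.9.2 concedes two limits of matching, namely unmatched patients and unobserved covariates. It then states "there are no superior alternative methods to adjust for differences in populations among the various clinical trials to enhance the robustness of the results". The checklist in Appendix A marks discussion of residual or unmeasured confounding (12.1.3) and of information bias (12.1.2) as not applicable.

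**The concern.** Matching can balance measured patient characteristics between two regimens. It cannot separate regimen from trial when every trial supplies only one of the two. Whatever differs between the Kd27 and Kd56 trials beyond List 1, such as setting, infusion time, assessment rules or grading, goes into the estimate together with dose.

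The result is meant to inform the choice of regimen, and Section 11 says the report goes to the FDA as a regulatory requirement. Without a statement that the contrast is wholly between trials, a reader would take a matched hazard ratio with a confidence interval as the effect of dose. The Kd56 side rests on two trials, one of which supplies three quarters of its subjects. Nothing described in the protocol is aimed at showing how far the answer depends on that one trial.

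**Working it through.** **1. Reproduce the plan's counts (Tables 2 and 3).**

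| Set | Kd27 | Kd56 | Kd total |
|---|---|---|---|
| Primary | 20140355: 235; 20140242: 123; 20140120: 20; 2011-002: 205. Sum 583 | 20160275: 153; 20130398: 463. Sum 616 | 1,199 from 6 trials |
| Sensitivity | primary + 20140122: 3. Sum 586 | primary + 20130393: 8 + 20130401: 3. Sum 627 | 1,213 from 9 trials |

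Both totals agree with the protocol. The Kd27 and Kd56 trial lists have no trial in common in either set (4 versus 2 trials, then 5 versus 4). A trial fixed effect, or stratification by trial, therefore cannot identify Kd56 versus Kd27, because every stratum would hold a single regimen.

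**2. Trial-level differences visible in Table 1.**
- Infusion time. Kd56: both trials at 30 minutes, 616/616. Kd27: only 20140242 at 30 minutes, 123/583 = 21%. The other 460/583 = 79% had 10 minutes or less. Section 5.1 itself ties the 56 mg/m² finding to giving it "when infused over a duration of 30 minutes instead of 10 minutes".
- Setting and prior therapy. 205/583 = 35% of Kd27 come from 2011-002, an expanded access program that requires at least 4 prior therapies and lists safety as its objective. 463/616 = 75% of Kd56 come from 20130398, which allows 1 to 3. Number of prior lines is in List 1, but these two blocks do not overlap on it by eligibility. Expanded access as a setting is not in List 1.
- Outcome rules. PFS, ORR and CTCAE criteria are each trial's own (Section 7.7.2.4). The protocol does not print them, so a difference is possible but not shown.

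**3. What the sensitivity analysis adds.** 1,213 − 1,199 = 14 Kd subjects, and 14/1,213 = 1.2%. By regimen this is 3/586 = 0.5% and 11/627 = 1.8%. All six primary Kd trials stay in, so the set cannot show dependence on any one of them.

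**4. Illustration of what an interval without a trial component omits.** This is not an estimate for this study. The between-trial SD of the log hazard (tau) and the 500 PFS events are assumptions, and the weights are the Table 2 shares before matching.
- Sum of squared shares, Kd27: (235² + 123² + 20² + 205²)/583² = 112,779/339,889 = 0.332, or about 3.0 effective trials.
- Kd56: (153² + 463²)/616² = 237,778/379,456 = 0.627, or about 1.6 effective trials.
- Var(log HR) = 4/events + tau² × (0.332 + 0.627). Sampling SE = 2/√500 = 0.089.
- Coverage = 2Φ(1.96 × sampling SE / total SE) − 1.

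| Assumed tau | Total SE | Ratio to sampling SE | Coverage of nominal 95% CI |
|---|---|---|---|
| 0.05 | 0.102 | 1.14 | 91% |
| 0.10 | 0.133 | 1.48 | 81% |
| 0.15 | 0.172 | 1.92 | 69% |
| 0.20 | 0.215 | 2.41 | 58% |

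With 200 to 583 matched pairs and 60 to 80% events instead, coverage is 72 to 88% at tau 0.10 and 47 to 72% at tau 0.20.

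**The case against.** The strongest reply has five parts.

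- **The SAP is not at hand.** The variance method for the hazard and odds ratios and the CMH strata are left to it. A reader might infer that these intervals certainly ignore trial, or that a trial-stratified CMH is planned and will fail. The protocol supports neither inference. This stands.
- **Era and prior lines are partly handled.** Both are in List 1, the caliper drops subjects with no near match, Section 7.9.2 concedes that loss, and subgroups by these variables are planned. This also stands. No enrolment years are given, so it would go too far to say that some years have no counterpart in the other regimen. But these steps act on measured patient covariates, and the setting and conduct of a trial are not among them.
- **Infusion time may be part of the regimen.** The objective compares regimens, and Section 5.1 describes 56 mg/m² over 30 minutes as one. That is a fair reading. In that case the result still cannot be attributed to dose alone, which is the wording the conclusion needs. An analysis of Kd56 against 20140242 only, to equalise infusion time, would bring problems of its own, since that is a single-arm trial in China. It is at most an optional display.
- **No better adjustment exists.** With no shared trial, no method separates regimen from trial, and a random trial effect with four versus two trials would be poorly estimated. This is correct. It is a reason to disclose the nesting, and the sentence in Section 7.9.2 offers reassurance instead.
- **The study is descriptive and post hoc.** This lowers the stakes, and non-randomisation and unobserved covariates are disclosed. But ratios with intervals, summarised as favourable or unfavourable, will still be read as comparisons.

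**Conclusion.** The point holds, on the protocol's own tables. Regimen is fully nested in trial for Kd27 versus Kd56 in both analysis sets. Matching on List 1 leaves trial-level differences in the contrast. Section 7.9.2 does not disclose this, and the protocol's one sensitivity analysis (14 added Kd subjects, 1.2%) could not reveal dependence on a single trial. These facts need no assumption.

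The size of any bias or undercoverage is not known. The range of about 91% down to 58% rests on an assumed tau of 0.05 to 0.20, an assumed 500 events and pre-matching weights. Matching will change those weights, in a direction that cannot be predicted from the protocol. A reader might infer that the planned intervals are shown to be too narrow by these factors, or that endpoint definitions and CTCAE versions are shown to differ by regimen. The protocol establishes neither.

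The point does not carry over to K27 versus Kd27. Those regimens share 2011-002 in the primary set (105 and 205 subjects), and also 20140120 and 20140122 in the sensitivity set.

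**What to change.** For Kd27 versus Kd56:

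1. Add leave-one-trial-out estimates of the HR, OR and RR, re-matching after each removal, and the eight trial-pair estimates (4 × 2). Say in advance that pairs with 20140120 (20 subjects) will be very imprecise, and that removing either Kd56 trial leaves only one.
2. Before outcomes are seen, tabulate year of initiation and number of prior lines by regimen and trial. After matching, report how many subjects each trial contributes.
3. State beside each confidence interval that it excludes between-trial variation, unless the SAP already has a trial component.
4. In Section 7.9.2, replace the sentence that no superior method exists with a statement that regimen is nested in trial, so the result is a between-trial contrast and not an isolated dose effect. Bring checklist items 12.1.2 and 12.1.3 into line.

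This takes a few extra model runs, two tables and some wording, with no new data. The price is a more qualified and possibly less favourable conclusion.

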7.9.3 Limitations Due to Missing Data and/or Incomplete Data

As previously noted, the implementation of these studies spanned nearly a decade, whereby the understanding of the myeloma disease has greatly improved. Despite special consideration, data for particular variables in several clinical trials may not exist. For example, as the predictors for outcomes in MM remain complex, the data collection

for two cardiovascular parameters of tobacco exposure and family history of early coronary artery disease have be inconsistent and thus will be excluded. Also, given the recent recommendations for FISH analysis, there would be no data for this clinical parameter of chromosomal abnormalities in earlier years of clinical trials. With the anticipate large volume of unknown data, this clinical parameter will be excluded. These parameters have been excluded to avoid large volumes of empty data fields due to non-existent data that would jeopardize the integrity of the analyses. To address data that is missing (versus non-existent data), please see [Section 7.7.2.2](#).

7.10 Other Aspects

For additional details, please refer to the SAP.

8. Protection of Human Subjects

8.1 Informed Consent

No study subjects will be contacted for the analysis.

8.2 Institutional Review Board/Independent Ethics Committee (IRB/IEC)

This study is a retrospective analysis of existing data; therefore, IRB approval is not necessary.

8.3 Subject Confidentiality

This protocol will comply with all applicable laws regarding subject privacy. No direct subject contact or collection of additional subject data will occur. Only anonymous data will be used for the analysis. Results will be in tabular form and aggregate analyses that omit subject identification. Any publications and reports will not include subject identifiers.

9. Collection, Recording, and Reporting of Safety Information and Product Complaints

Reporting of individual adverse events (AE), product complaints, and other safety findings is not applicable for this pooled retrospective post-hoc analysis, as the safety data from the studies identified have been previously reported to regulatory agencies, institutional review boards, and ethics committees in accordance with local regulations and routine pharmacovigilance practices. No new safety data will be collected or analyzed to complete the objectives of this study.

10. Administrative and Legal Obligations

Amgen may amend the protocol at any time. Amgen reserves the right to terminate the study at any time.

11. Plans for Disseminating and Communicating Study Results

As a regulatory requirement, this report will be submitted to the FDA at the agreed upon timelines; otherwise, there are no current plans to submit results for publication.

12. References

- Austin PC. A comparison of 12 algorithms for matching on the propensity score. *Statistics in Medicine*. 2014;33:1057-1069.

Appendix A. ENCePP Checklist for Study Protocol

Study title: Comprehensive Analysis of Clinical Parameters that May Inform the Choice of Dose Regimen for Carfilzomib 20/27mg/m² or 20/56mg/m² With and Without Dexamethasone

EU PAS Register® number:
Study reference number (if applicable):

Section 1: Milestones	Yes	No	NA	Section Number
1.1 Does the protocol specify timelines for				
1.1.1 Start of data collection ¹		X		
1.1.2 End of data collection ²		X		
1.1.3 Progress report(s)			X	
1.1.4 Interim report(s)			X	
1.1.5 Registration in the EU PAS Register®		X		
1.1.6 Final report of study results.		X		

Section 2: Research question	Yes	No	NA	Section Number
2.1 Does the formulation of the research question and objectives clearly explain:				
2.1.1 Why the study is conducted? (eg, to address an important public health concern, a risk identified in the risk management plan, an emerging safety issue)	X			5.2
2.1.2 The objective(s) of the study?	X			6.1, 6.2, 6.3
2.1.3 The target population? (ie, population or subgroup to whom the study results are intended to be generalised)	X			7.2.1.1
2.1.4 Which hypothesis(-es) is (are) to be tested?			X	7.7.2.1
2.1.5 If applicable, that there is no a priori hypothesis?			X	

Section 3: Study design	Yes	No	NA	Section Number
3.1 Is the study design described? (eg, cohort, case-control, cross-sectional, other design)	X			7.1

¹ Date from which information on the first study is first recorded in the study dataset or, in the case of secondary use of data, the date from which data extraction starts.

² Date from which the analytical dataset is completely available.

Section 3: Study design		Yes	No	NA	Section Number
3.2	Does the protocol specify whether the study is based on primary, secondary or combined data collection?	X			7.1
3.3	Does the protocol specify measures of occurrence? (eg, rate, risk, prevalence)	X			7.7.1, 7.7.1.1, 7.7.2, 7.7.2.5
3.4	Does the protocol specify measure(s) of association? (eg, risk, odds ratio, excess risk, rate ratio, hazard ratio, risk/rate difference, number needed to harm (NNH))	X			7.7.2.4
3.5	Does the protocol describe the approach for the collection and reporting of adverse events/adverse reactions? (eg, adverse events that will not be collected in case of primary data collection)			X	9

Section 4: Source and study populations		Yes	No	NA	Section Number
4.1	Is the source population described?	X			7.2.1.1
4.2	Is the planned study population defined in terms of:				
	4.2.1 Study time period			X	
	4.2.2 Age and sex			X	
	4.2.3 Country of origin			X	
	4.2.4 Disease/indication	X			7.2.1.1
	4.2.5 Duration of follow-up			X	
4.3	Does the protocol define how the study population will be sampled from the source population? (eg, event or inclusion/exclusion criteria)	X			7.2.1.1

Section 5: Exposure definition and measurement		Yes	No	NA	Section Number
5.1	Does the protocol describe how the study exposure is defined and measured? (eg, operational details for defining and categorising exposure, measurement of dose and duration of drug exposure)	X			7.7.2.3
5.2	Does the protocol address the validity of the exposure measurement? (eg, precision, accuracy, use of validation sub-study)			X	
5.3	Is exposure categorised according to time windows?			X	
5.4	Is intensity of exposure addressed? (eg, dose, duration)	X			7.7.2.3
5.5	Is exposure categorised based on biological mechanism of action and taking into account the pharmacokinetics and pharmacodynamics of the drug?			X	
5.6	Is (are) (an) appropriate comparator(s) identified?			X	

Section 6: Outcome definition and measurement		Yes	No	NA	Section Number
6.1	Does the protocol specify the primary and secondary (if applicable) outcome(s) to be investigated?	X			7.3, 7.7.2.4
6.2	Does the protocol describe how the outcomes are defined and measured?	X			7.7.2.4
6.3	Does the protocol address the validity of outcome measurement? (eg, precision, accuracy, sensitivity, specificity, positive predictive value, use of validation sub-study)			X	
6.4	Does the protocol describe specific outcomes relevant for Health Technology Assessment? (eg, HRQoL, QALYs, DALYS, health care services utilisation, burden of disease or treatment, compliance, disease management)			X	

Section 7: Bias		Yes	No	NA	Section Number
7.1	Does the protocol address ways to measure confounding? (eg, confounding by indication)	X			7.9.1.1
7.2	Does the protocol address selection bias? (eg, healthy user/adherer bias)	X			7.9.2
7.3	Does the protocol address information bias? (eg, misclassification of exposure and outcomes, time-related bias)	X			7.3.4

Section 8: Effect measure modification	Yes	No	NA	Section Number
8.1 Does the protocol address effect modifiers? (eg, collection of data on known effect modifiers, sub-group analyses, anticipated direction of effect)	X			7.7.2.5.1

Section 9: Data sources	Yes	No	NA	Section Number
9.1 Does the protocol describe the data source(s) used in the study for the ascertainment of:	X			7.4, 7.6.1
9.1.1 Exposure? (eg, pharmacy dispensing, general practice prescribing, claims data, self-report, face-to-face interview)	X			7.4, 7.6.1
9.1.2 Outcomes? (eg, clinical records, laboratory markers or values, claims data, self-report, patient interview including scales and questionnaires, vital statistics)	X			7.4, 7.6.1
9.1.3 Covariates and other characteristics?	X			7.4, 7.6.1
9.2 Does the protocol describe the information available from the data source(s) on:				
9.2.1 Exposure? (eg, date of dispensing, drug quantity, dose, number of days of supply prescription, daily dosage, prescriber)	X			7.4, 7.6.1
9.2.2 Outcomes? (eg, date of occurrence, multiple event, severity measures related to event)	X			7.4, 7.6.1
9.2.3 Covariates and other characteristics? (eg, age, sex, clinical and drug use history, co-morbidity, co-medications, lifestyle)	X			7.4, 7.6.1
9.3 Is a coding system described for:				
9.3.1 Exposure? (eg, WHO Drug Dictionary, Anatomical Therapeutic Chemical (ATC) Classification System)			X	
9.3.2 Outcomes? (eg, International Classification of Diseases (ICD), Medical Dictionary for Regulatory Activities (MedDRA))	X			7.7.3
9.3.3 Covariates and other characteristics?	X			7.4, 7.6.1
9.4 Is a linkage method between data sources described? (eg, based on a unique identifier or other)	X			7.4, 7.6.1

Section 10: Analysis plan	Yes	No	NA	Section Number
10.1 Are the statistical methods and the reason for their choice described?	X			7.7.2, 7.7.2.1, 7.7.2.2, 7.7.2.4, 7.7.2.5, 7.7.2.5.1 7.7.3
10.2 Is study size and/or statistical precision estimated?			X	7.5
10.3 Are descriptive analyses included?	X			7.7.2, 7.7.2.1, 7.7.2.3,
10.4 Are stratified analyses included?			X	
10.5 Does the plan describe methods for analytic control of confounding?	X			7.9.1.1
10.6 Does the plan describe methods for analytic control of outcome misclassification?			X	
10.7 Does the plan describe methods for handling missing data?	X			7.7.2.2, 7.9.3
10.8 Are relevant sensitivity analyses described?	X			7.7.2.5

Section 11: Data management and quality control	Yes	No	NA	Section Number
11.1 Does the protocol provide information on data storage? (eg, software and IT environment, database maintenance and anti-fraud protection, archiving)	X			7.6.1
11.2 Are methods of quality assurance described?	X			7.6, 7.6.2, 7.8
11.3 Is there a system in place for independent review of study results?			X	

Section 12: Limitations		Yes	No	NA	Section Number
12.1	Does the protocol discuss the impact on the study results of:				7.9.2
	12.1.1 Selection bias?	X			
	12.1.2 Information bias?			X	
	12.1.3 Residual/unmeasured confounding? (eg, anticipated direction and magnitude of such biases, validation sub-study, use of validation and external data, analytical methods).			X	
12.2	Does the protocol discuss study feasibility? (eg, study size, anticipated exposure uptake, duration of follow-up in a cohort study, patient recruitment, precision of the estimates)	X			5.3

Section 13: Ethical/data protection issues		Yes	No	NA	Section Number
13.1	Have requirements of Ethics Committee/ Institutional Review Board been described?	X			8.2
13.2	Has any outcome of an ethical review procedure been addressed?			X	
13.3	Have data protection requirements been described?	X			7.4, 7.6, 7.6.1, 8.3

Section 14: Amendments and deviations		Yes	No	NA	Section Number
14.1	Does the protocol include a section to document amendments and deviations?	X			10

Section 15: Plans for communication of study results		Yes	No	NA	Section Number
15.1	Are plans described for communicating study results (eg, to regulatory authorities)?	X			11
15.2	Are plans described for disseminating study results externally, including publication?			X	11
